1) Protocol Title

Addressing Tobacco Health Disparities via Group Intervention

2) Objectives*

Purposes and aims: (1) Examine the effects of CBT for smoking cessation on perceived stress and depressive symptoms in a racially/ethnically diverse sample; (2) test the efficacy of CBT for eliminating smoking cessation disparities; and (3) Examine physiological distress as an underlying mechanism for the effects of CBT on racial/ethnic minority smokers (exploratory).

3) Background*

Significance: Tobacco smoking is robustly associated with significant morbidity and mortality, from conditions such as cancer, diabetes, cardiovascular disease, and hypertension. Pervasive smoking-related health disparities exist across racial/ethnic and socioeconomic status (SES) groups. The most established disparities are observed in comparisons of African Americans and Whites, though evidence demonstrates disparities across populations of smokers.

The importance of reducing tobacco-associated health disparities between cannot be understated. Racial/ethnic minority smokers are less likely to quit successfully, even in the context of treatment. Perceived stress and depressive symptoms are known barriers to smoking cessation, yet have virtually been ignored in the disparities literature.

Racial/ethnic minority smokers tend to have elevated distress levels, which may contribute to disparities in cessation and health. Cognitive behavioral therapy (CBT) for cessation addresses these concerns and has the potential to reduce or eliminate disparities. Our preliminary studies, conducted in our established research clinic, found race/ethnic differences in baseline perceived stress and depressive symptoms. Following CBT, these differences were no longer present. Moreover, the lack of disparity in cessation appeared to be driven by the positive change in stress and depressive symptoms. This study will be the first RCT to test the impact of CBT on smoking cessation disparities.

4) Inclusion and Exclusion Criteria*

Inclusion criteria for this study include: (1) self-identify as African American/Black, Hispanic (any race), or White non-Hispanic; (2) smoke at least 5 cigarettes/day or CO reading of at least 8 ppm; (3) be over age 18; and (4) speak/read English and/or Spanish.

Exclusion criteria include: (1) contraindications for transdermal nicotine patch therapy (TNP); (2) cognitive or mental health impairment that inhibits group treatment; (3) currently being treated for smoking cessation, alcoholism, or illicit drug use; (4) unable to attend sessions; (5) indications that participant is not appropriate for the study (e.g., aggressive, intoxicated, disruptive, visibly ill); (6) does not self-identify as African American, Hispanic, or White (non-Hispanic).

Withdrawal of Subjects

The following are reasons for withdrawal of subjects from the study:

- A subject does not meet the eligibility criteria, (the subject will be considered a screen failure).
- A subject withdraws informed consent.
- A subject dies during protocol participation or
- A study investigator decides the subject should be withdrawn from the study (e.g. subject non-compliance)

Regardless of reason for withdrawal, once a subject has been randomized to a study arm, an intention to treat analysis will be performed.

Procedures Involved

This behavioral intervention study includes a baseline assessment, randomization to one of two conditions, and 4 subsequent assessments. Screening may occur in person or over the telephone. Eligible participants may be scheduled for an appointment to attend orientation/baseline assessment. Time permitting prior to the appointment, we may attempt to mail a confirmation letter and/or complete reminder contacts (telephone calls, text messages, email) leading up to the appointments.

Assessments. At the baseline visit, eligible participants will provide written informed consent, and complete some or all of the baseline measures (described below). They may also be asked to complete intra-treatment assessments during the 8 sessions. Follow-up assessments (called “reunions”) may occur at the end-of-therapy (EOT), and 3, 6, and 12-month follow-ups. The full assessment (at baseline) may require approximately 90 minutes to complete. Intra-treatment assessments may require 5 minutes, and follow-ups may require 60 minutes. The questionnaires may be completed (fully or in part) electronically using iPads/computers or on paper. Skip patterns may be built into the measures to decrease participant burden. All items are voluntary, thus participants may select an answer for each item before moving forward, and will have the option of selecting ‘I would rather not say’ on the electronic version or skipping items as desired. Surveys in either electronic or paper format will use identification numbers rather than identifying information.

Participants may complete some or all of the following measures:

Questionnaires: A standard demographic questionnaire assessing race, ethnicity, nativity, age, education, employment status, health insurance, marital status, and number of children. Measures may also include current medications, medical history (e.g., diabetes, hypertension, chronic back pain, arthritis, emphysema, and asthma), height, weight, smoking history, nicotine dependence, readiness to quit smoking, perceived stress, depressive symptoms, alcohol use, ethnic discrimination, nicotine withdrawal and urges to smoke, social support, daily hassles, e-cigarette use, sleep quality, intervention evaluations, group cohesion, smoking pattern, history of substance dependence and treatment, and use of other tobacco products and pharmacotherapies.

Bio-verification: Saliva cotinine levels may be assessed at baseline, and to confirm self-reported cessation at the 3, 6, and 12-month follow-ups. Research staff will be trained in the U.S. Centers for Disease Control (CDC) guidelines for transport of biological

specimens within the United States. The CBT intervention includes carbon monoxide (CO) testing at each treatment session to provide immediate feedback to participants regarding the benefits of cessation.

Salivary cortisol: At each assessment point, we may collect saliva samples for cortisol analyses. Participants who agree will be provided with the needed materials and trained in saliva collection procedures at orientation and prior to assessments. They may be asked to collect saliva up to 4 times throughout the day. Saliva samples will be stored in the lab freezers. At the time of collection, we will ask participants to record hours of sleep, food consumption, and exercise within the past hour.

Randomization. Participants may be randomly assigned to one of 2 conditions. In the first condition, *Group Cognitive Behavioral Therapy for Smoking Cessation (CBT)*, participants may receive 8 group sessions and eight weeks of TNP [21mg (4 weeks), 14mg (2 weeks), and 7mg (2 weeks)]. The four-week CBT protocol includes 4 sessions during week 1, 2 sessions during week 2, 1 session during week 3, and 1 session during week 4. We will request that participants attend every session; however, we recognize that this will not always be feasible. CBT is intended to guide participants through the cessation process and teach relapse prevention skills. Sessions may include a functional analysis of smoking patterns, environmental cues, and motivation for change, and cover nicotine addiction and withdrawal, health consequences, benefits of cessation, stress management, negative affect, alcohol use, triggers, coping responses, cognitive restructuring, social support, decision making, weight control, and physical activity. In the second condition, *General Health Education*, participants may receive sessions including didactic information on tobacco-associated morbidities, such as heart disease, diabetes, and hypertension. Content may include PowerPoint-delivered lectures on the prevalence, etiology, basic pathology, symptom patterns, and treatment of the conditions, and discussion questions designed to facilitate learning and interest. Smoking cessation specific topics will not be addressed, and coping skills will not be provided. Participants will be allowed to share feelings regarding smoking (if they mention them) and general questions will be answered, although no specific behavioral quitting advice will be provided (i.e., they will be encouraged to adhere to the TNP protocol). The groups in both conditions are expected to require 90-120 minutes, depending on group size. Sessions may be audio or video taped.

Participants will be paid for completing assessments, baseline (\$20), EOT (\$30), 3-month (\$40.00), 6-month (\$50.00), and 12-month (\$50.00), prorated by half for incomplete assessments. Funds permitting, participants may also receive reimbursement for transportation and light refreshments during visits. We anticipate that data collection may occur within a 4-year period, although this may vary depending on recruitment progress.

5) Data and Specimen Banking*

N/A

6) Data Management*
Statistical Analysis

Descriptive statistics such as frequencies, percentages, means, medians, standard deviations, and interquartile ranges may be tabulated to describe the study sample.

Associations between variables and intervention effects may be assessed with Wilcoxon/Kruskal-Wallis tests, Chi-squared/Fisher exact tests, analyses of variance, multiple regression, generalized linear mixed models, and logistic regression.

Data may be collected using the University of Miami Qualtrics survey program and stored on password-protected university servers. Surveys collected on paper will be entered by members of the research team into password protected data files. Access to the files containing the survey and survey responses is restricted and only study personnel will be given access to these files. Identifying information will not be collected with electronic or paper questionnaires. Data published from this survey will be presented in group form, so that individual participant data is not identifiable. Data may be stored for up to five years following publication of findings.

Guidelines for Adverse Events (AEs) and Smoking Cessation Rates

We anticipate few adverse events due to study participation. Abstinence from smoking may lead to withdrawal symptoms, including irritability, anxiety, restlessness, sadness, and difficulty concentrating. These symptoms are expected and manageable and most resolve in two to six weeks in abstinent smokers. Withdrawal can be attenuated by the use of nicotine replacement therapy (NRT). The NRT to be administered in this study is FDA-approved and has demonstrated adverse side effects in only a minority of users. To ensure the safety of subjects, any persons who report adverse side effects from NRT will be advised to discontinue use and encouraged to visit their private doctor or referred to the emergency room. Any persons who report problematic nicotine withdrawal (e.g., depression) will be assessed for severity by the [name], who is a clinical psychologist. If the participant's depression is greater than that expected due to typical nicotine withdrawal or is causing significant impairment in functioning, the subject will be referred for services at the Psychological Services Center—the Psychology Department's on-campus training clinic, or to a community mental health provider. In the case of serious adverse events (SAEs) or other untoward occurrence, the PI will notify the Data and Safety Monitoring Committee (DSMC), the Office of Research, and the IRB via telephone at the time of the incident, followed by a detailed written account of the nature and scope of the events and the reason(s) for their occurrence. The activities of the project will be suspended, pending a full IRB review. The IRB will follow-up with appropriate action and the research will proceed only with written IRB approval. In the event of serious adverse events (SAEs) or incidents, the Office of Research and DSMC will take the necessary steps to document the events in writing to our regulatory boards.

SAEs: The DSMC will engage in expedited reviews for any occurrences meeting the FDA definition of SAEs – i.e., any fatal event, acute life-threatening event, permanently or substantially disabling event, event requiring participant hospitalization, or any congenital anomaly. These reviews will determine whether the event poses a significant hazard, side effects, or requires precaution. Any SAE will be required to be reported to the DSMC, irrespective of its perceived relatedness to the study. Reports will include a description of the event and its outcome, related medications, the participant's medical history and current conditions, and all relevant clinical data. Notification by e-mail, and FAX transmittal of SAE's and all related documents will be sent to the DSMC within 2 days of the occurrence.

Smoking cessation rates are assessed via Qualtrics at end of counseling (EOC) and follow-up time points.

7) Risks to Subjects*

The risks to subjects, immediate and long range, are considered minimal. Study participants will be asked to complete relatively benign questionnaires and before and after receiving behavioral treatment plus nicotine replacement for smoking cessation. It is possible that subjects might become psychologically distressed while completing questionnaires or be dissatisfied with the intervention. They will be provided with transdermal nicotine patches that are available over-the-counter and required to indicate whether they have any health conditions that may negatively interact with the patches.

To minimize the risk of psychological distress due to questionnaire completion, the measures do not contain private or potentially embarrassing items, and are limited to 90 minutes completion time per assessment. To minimize the risk of dissatisfaction with the intervention, we will use an established intervention that has high efficacy. To minimize risks associated with the nicotine patches, subjects will be provided with thorough education of the indications for the nicotine patch, possible side effects, and known health conditions that preclude patch use. The patches are available over the counter; thus, they do not pose a significant health risk to most people. They contain minimal amounts of nicotine (which are much less than they get from smoking), and are absent the remaining 7,000 toxins contained in cigarettes. In addition, we will refer patients with a questionable medical history to their family physician or to Jackson Memorial Hospital or Tampa General (which accept uninsured patients) for consultation.

8) Potential Benefits to Subjects*

9) Individual subjects can potentially benefit from participating in the study because they may be exposed to one of two established smoking cessation treatments plus transdermal nicotine patch therapy. Thus, all participants will have the opportunity to make a quit attempt and the possibility of long-term smoking cessation. This is associated with a number of additional benefits including improved health, economic savings, the confidence and happiness associated with becoming an ex-smoker, and eliminating the second-hand smoke exposure to others.

10) Vulnerable Populations*

This research study does not include vulnerable populations.

11) Setting

The primary study site is the University of Miami Clinical Research Building, with offices on the Miller School of Medicine campus, and in the Flipse building on the Coral Gables campus. The Miami site will also recruit participants in Broward County and conduct groups at several Broward locations for participant convenience. The second study site is the Tobacco, Research, and Intervention Program (TRIP) at the H. Lee Moffitt Cancer

Center and Research Institute in Tampa, FL. Participants may also be recruited and screened at community events and may be scheduled to come to the lab at a later date. Community-based recruitment is intended to diversify the sample, and will reduce barriers to on-campus participation.

12) Resources Available

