Participant recruitment may occur using several methods, including radio and newspaper stories and advertisements, community events (e.g., health fairs), neighborhood canvassing, email, online social-media and advertising sites, and flyers and post-cards distributed throughout the community (e.g., churches, Laundromats, businesses, physicians’ offices, health centers/clinics). Recruitment may also take place at other medical sites (e.g., Broward Health organization, and UHealth regional sites) through patient referrals, community outreach, or direct referrals to the Research staff. After calling the telephone

number provided in the advertisements or being identified in person, RAs may explain the study to participants (paraphrasing from a script) and conduct screening for eligibility.

Participants may be given small tokens of appreciation, such as water bottles, wallets, or bags.

15) Local Number of Subjects

We anticipate screening up to 1000 subjects and enrolling up to 500 to complete the study. Moffitt Cancer Center will enroll 150 subjects. Moffitt's enrollment numbers are not included in this protocol, being as it is stated in their own IRB protocol.

16) Confidentiality

Contact information for participants scheduling appointments to participate on site may be recorded over the telephone and stored in a password encrypted database. Following study completion, contact information may be deleted from the database. Only the PI and study personnel may have access to the database. Survey data may be collected and stored on University of Miami and H. Lee Moffitt Cancer Center password protected servers using electronic survey software. Assessment responses will not include identifying information. Only select study personnel may have administrative access to the survey data. Personnel with access must log onto the system with a username and password. Data may be maintained for five years post study publication.

17) Provisions to Protect the Privacy Interests of Subjects

Study participation is completely voluntary and confidential, which is explained during the informed consent process. Several RAs will recruit, schedule, and collect information from participants. They may elect to interact with (or not) any of the study staff. The questionnaires may be self-administered; however staff will be available to assist participants as needed. If desired and space-permitting, participants may be allowed to complete the assessment in private.

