18) Consent Process

Participants will undergo screening for enrollment into the study. We are requesting a waiver of documentation of consent for this portion only as it is done via phone or in person; however, this is minimal risk and consent is not required outside of the research setting to ask the screening questions.

Informed consent may be obtained prior to confirming eligibility to participate in the study during the baseline visit. Consent will be obtained by the PI or key personnel (trained Research Associates and clinical psychology graduate students).

19) Process to Document Consent in Writing

Participants will be given an informed consent form. Study staff will be available to explain the assessments to participants and answer any questions they have about participation. Participants will be provided with copies of the consent document.

20) Data & Safety Monitoring Committee Oversight

The Sylvester Comprehensive Cancer Center (SCCC) Data and Safety Monitoring Committee (DSMC) will monitor this clinical trial according to the Cancer Center's Data and Safety Monitoring Plan (DSMP). In its oversight capacity, the DSMC bears responsibility for suspending or terminating this study.

DSMC oversight of the conduct of this trial includes ongoing review of adverse event data, and periodic review of self-reported smoking cessation rates. The guidelines appearing in Section #6 are offered for DSMC consideration in assessing adverse events and self-reported smoking cessation rates. In addition, the DSMC will review reports from all audits, site visits, or study reviews pertaining to this clinical trial and take appropriate action.

21) Monitoring, Auditing, and Inspecting

The investigator will permit trial-related monitoring, quality audits, and inspections by, government regulatory authorities, of all trial-related documents (e.g., source documents, regulatory documents, data collection instruments, case report forms). The investigator will ensure the capability for inspections of applicable trial-related facilities. The investigator will ensure that the trial monitor or any other compliance or QA reviewer is given access to all trial-related documents and trial-related facilities. Participation as an investigator in this trial implies the acceptance of potential inspection by government regulatory authorities.

22) Quality Assurance and Quality Control

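### Intention-to-treat is promised whatever the reason for withdrawal, but nothing says outcomes are still collected after an investigator withdraws a randomized participant for non-compliance

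*Combined protocol and SAP*

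**What the plan says.** Withdrawal of Subjects lists four reasons for withdrawal from the study: ineligibility (treated as screen failure), withdrawn consent, death, and an investigator's decision. The last reads "A study investigator decides the subject should be withdrawn from the study (e.g. subject non-compliance", and non-compliance is its only example. The sentence after the list is: "Regardless of reason for withdrawal, once a subject has been randomized to a study arm, an intention to treat analysis will be performed".

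The list also covers people who have not been randomized. Screen failure is on it, and section 18 (Consent Process) notes: "Informed consent may be obtained prior to confirming eligibility to participate in the study during the baseline visit". The point here concerns randomized participants only.

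Procedures Involved sets the schedule: "This behavioral intervention study includes a baseline assessment, randomization to one of two conditions, and 4 subsequent assessments". The four are end of therapy (EOT) and 3, 6 and 12 months. Neither that section nor Withdrawal of Subjects says whether they go on after an investigator's withdrawal. Neither has a category for stopping sessions or patches while remaining in follow-up. The Statistical Analysis text in section 6 lists candidate methods and gives no rule for missing outcomes.

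**The concern.** An intention-to-treat comparison needs everyone kept in the assigned arm and outcomes observed for them. The plan commits to the first only. Of the four grounds, investigator withdrawal is the one most within the study team's control. Screen failure should come before randomization, and death and withdrawn consent cannot be overridden.

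Non-compliance arises after randomization and may well be related to smoking outcome. If people withdrawn for it are no longer assessed, the missing outcomes come from a selected group. Should that group differ in size between arms, the comparisons of cessation, perceived stress and depressive symptoms can be biased. Should it also differ by race/ethnicity, so can the disparity comparison in aim 2. Data that were never collected cannot be recovered at analysis.

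**Working it through.** **No plan figure to reproduce.** The documents give no expected cessation, withdrawal or dropout rate, and no alpha or power. The calculation below is an illustration. Only the enrolment ceiling of 500 (section 15) and the payments come from the protocol.

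**Assumed inputs.** No true effect; abstinence p = 0.20 in both arms; 500 participants split equally, so n = 250 per arm; share withdrawn and not assessed w1 and w2; abstinence q among those withdrawn; two-sided 5% test.

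**Formulas, withdrawn participants excluded.**
- Observed abstinence in an arm: (p − w·q)/(1 − w). Call the two results a and b, with d = a − b.
- SE = √[a(1 − a)/(n(1 − w1)) + b(1 − b)/(n(1 − w2))].
- Actual error = Φ(−1.96 + d/SE) + Φ(−1.96 − d/SE).

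Worked example, w1 = 0.10, w2 = 0.05, q = 0.02 (25 against 12.5 people withdrawn):
- a = (0.20 − 0.002)/0.90 = 0.2200
- b = (0.20 − 0.001)/0.95 = 0.2095
- d = 1.05 points, SE = 3.82 points, d/SE = 0.28, error = 5.87%

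| Withdrawn | q | d (points) | SE (points) | Error |
|---|---|---|---|---|
| 4% vs 2% | 0.02 | 0.38 | 3.67 | 5.12% |
| 4% vs 2% | 0.05 | 0.32 | 3.66 | 5.09% |
| 10% vs 5% | 0.02 | 1.05 | 3.82 | 5.87% |
| 10% vs 5% | 0.05 | 0.88 | 3.80 | 5.61% |
| 10% vs 5% | 0.10 | 0.58 | 3.78 | 5.27% |
| 10% vs 5% | 0.15 | 0.29 | 3.75 | 5.07% |
| 20% vs 10% | 0.02 | 2.50 | 4.11 | 9.34% |
| 20% vs 10% | 0.05 | 2.08 | 4.07 | 8.04% |

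Every d favours the arm with more withdrawals, and d shrinks as q approaches 0.20.

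**Missing counted as smoking.** Observed abstinence is p − w·q, so d = −(w1 − w2)·q. At 10% versus 5% this is −0.10 points (q = 0.02) and −0.25 points (q = 0.05). If withdrawal is unrelated to outcome (q = 0.20), it is −1.0 point, while exclusion gives 0. Neither rule is free of bias in every case.

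**Effect of continued follow-up.** Suppose half of those withdrawn are still assessed, with similar abstinence in those reached and not reached. This halves w. At 10% versus 5%, the exclusion bias falls from 1.05 to 0.49 points (q = 0.02) and from 0.88 to 0.40 points (q = 0.05). Under missing = smoking the bias also halves, because d is proportional to w1 − w2.

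**Aim 2.** Assume three equal race/ethnic groups (500/6 ≈ 83 per arm in each), one group at 10% versus 5%, and a comparison group at 5% in both arms. The between-group contrast is biased by 0.88-1.05 points against an SE of about 9.2 points (error 5.10-5.15%), which is small relative to noise.

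**Payments for the four assessments** (Procedures Involved): 30 + 40 + 50 + 50 = $170 per person.

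**The case against.** The strongest reply is that the protocol never says assessment stops. The intention-to-treat sentence can be read as a commitment to keep such people in the trial's data, and staff may follow them up as a matter of course. This stands in part. The text is silent rather than self-contradictory, and the loss of outcomes is an inference from withdrawal being from the study. The consent pages and the text after the heading of section 12 were not available to this review. Even so, a statement about analysis does not instruct anyone to collect data.

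Three stronger readings are tempting, and the documents support none of them.

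- A reader might infer that compliance is judged differently by arm. The CBT description says "We will request that participants attend every session; however, we recognize that this will not always be feasible", and the General Health Education description says only that "they will be encouraged to adhere to the TNP protocol". These are unrelated statements: one is about attendance, the other about what staff say in place of quitting advice. The withdrawal list is common to both arms, and nothing indicates different rules.
- A reader might take the sentence "Smoking cessation rates are assessed via Qualtrics at end of counseling (EOC) and follow-up time points" as showing that remote assessment is already provided for. It names survey software. It does not say that participants complete the survey away from the site.
- A reader might quote an error rate of 8-9%. That needs 20% versus 10% withdrawn by investigators, very low abstinence among them, and their exclusion. Nothing in the documents points to such an imbalance, and the acceptance of missed sessions points, if anything, to few withdrawals on that ground.

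It is also fair to say that the absence of a missing-outcome rule affects all dropout, not just this route. That gap, like the undefined term non-compliance, is missing detail and does not carry this point.

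**Conclusion.** The point holds in a limited form. As written, the withdrawal rule allows a randomized participant to be taken out of the study for non-compliance, and the intention-to-treat promise does not secure that person's outcomes. On assumed rates the bias in the cessation comparison is about 0.3-0.4 points at 4% versus 2% withdrawn and 0.9-1.1 points at 10% versus 5%. The second is roughly a quarter of a standard error. Both figures assume that those withdrawn are excluded and that 2-5% of them are abstinent. The bias is smaller if they are abstinent more often, and absent if withdrawn participants are in fact still assessed. No size was worked out for perceived stress or depressive symptoms. Frequency is unknown. The change is worth making because it is cheap and can only be made prospectively. Priority: minor.

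**What to change.** In Withdrawal of Subjects, state that non-compliance with sessions or patches does not by itself end follow-up. State also that randomized participants who have not died or withdrawn consent for follow-up are still invited to the EOT, 3-, 6- and 12-month assessments and are analysed in their assigned arm. Record stopping the intervention separately from leaving follow-up, and report both by arm. When sessions or patches may be stopped is left to the sponsor.

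The Tampa site works under a separate protocol; section 15 says its "enrollment numbers are not included in this protocol, being as it is stated in their own IRB protocol". If that protocol has the same withdrawal rule, it needs the same wording.

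Cost: a few sentences, extra follow-up contacts, up to $170 in payments per affected participant, and saliva assays whose price the documents do not give. At the assumed 10% versus 5%, that is 250 × (0.10 + 0.05) = 37.5 people and at most 37.5 × 170 = $6,375 in payments. Any remote assessment would be a new procedure and could lack the cotinine confirmation planned at 3, 6 and 12 months, so self-reports obtained that way should be flagged as unverified.

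### Both conditions are delivered in groups, but the analysis section permits arm comparisons that ignore therapy group, and no text reviewed says it will be modelled

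*Combined protocol and SAP*

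**What the plan says.** The Randomization paragraph under Procedures Involved states that "Participants may be randomly assigned to one of 2 conditions". Delivery is then collective on both sides: "The groups in both conditions are expected to require 90-120 minutes, depending on group size". The education condition is interactive too, with "discussion questions designed to facilitate learning and interest". Assessments after baseline "may occur at the end-of-therapy (EOT), and 3, 6, and 12-month follow-ups". The list of possible questionnaires includes "intervention evaluations, group cohesion, smoking pattern".

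The only inferential sentence in the text reviewed is in section 6, Statistical Analysis. It covers associations in general as well as effects, and says that "intervention effects may be assessed with Wilcoxon/Kruskal-Wallis tests, Chi-squared/Fisher exact tests, analyses of variance, multiple regression, generalized linear mixed models", with logistic regression closing the list. It names no random effect, cluster variance, ICC or group identifier. It does not say which method serves which outcome.

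**The concern.** People treated together share a leader, a schedule, a place and each other's company, so their outcomes may be correlated. If they are, the variance of an arm difference includes a between-group part that independent-observation methods leave out. Standard errors are then too small, p-values too small and confidence intervals too narrow.

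The comparisons exposed are CBT against health education on cessation, perceived stress and depressive symptoms. An analyst could follow section 6 exactly and report them with overstated precision. Nothing in the plan would warn the reader or supply the variable needed to correct it.

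**Working it through.** **Inputs from the protocol.** Group delivery in both conditions (Randomization); up to T = 4 post-baseline assessments (Assessments); local enrolment of up to 500 (section 15). No sample-size or power calculation appears in the text reviewed, so there is no figure of the plan's to reproduce.

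**Assumed, because not stated.** Group size m of 5 to 12, ICC 0.01 to 0.05, two-sided 5% test, equal allocation. Further assumptions are given where used.

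**1. Arm comparison ignoring groups.** Design effect DE = 1 + (m − 1) × ICC. True type I error = 2 × [1 − Φ(1.96/√DE)]. Effective N = 500/DE; N does not enter the error rate.

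| m | ICC | DE | Type I error | Effective N |
|---|---|---|---|---|
| any | 0 | 1.00 | 5.00% | 500 |
| 5 | 0.01 | 1.04 | 5.46% | 481 |
| 10 | 0.01 | 1.09 | 6.05% | 459 |
| 10 | 0.05 | 1.45 | 10.36% | 345 |
| 12 | 0.05 | 1.55 | 11.54% | 323 |

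Simulation with 25 groups of 10 per arm agrees. At ICC 0.01 and 0.05, a chi-squared test rejects 6.2% and 10.0% of the time and a t-test 6.4% and 11.2%. A t-test on group means rejects 5.2% at both.

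**2. Mixed model with a participant effect only.** This would comply with section 6. Let r be the within-person correlation and ρ the correlation of the group effect over visits. The ICC of participant means over four visits is ICC × [ρ + (1 − ρ)/4] / [r + (1 − r)/4]. With m = 12, ICC 0.05 and r = 0.3, the denominator is 0.3 + 0.7/4 = 0.475:

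- ρ = 0: 0.05 × 0.25/0.475 = 0.0263; DE = 1.289; type I error 8.4%.
- ρ = r: 0.05; DE = 1.55; 11.5%.
- ρ = 1: 0.05/0.475 = 0.1053; DE = 2.158; 18.2%.

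At m = 5 and ICC 0.01 the three values are 5.2%, 5.5% and 6.0%. A participant effect does not stand in for a group effect.

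**3. Race-by-arm contrast ignoring groups.** Simulated with ICC 0.05, 10 to 12 per group and two thirds minority participants (assumed). Type I error is 4.6% to 4.7% when all groups are mixed. With 20%, 33% and 50% all-minority groups it is 5.4% to 5.6%, 5.8% to 6.1% and 7.3% to 7.6%. It reaches 9.9% to 10.9% only if every group is single-race. In mixed groups the group effect largely cancels from the contrast.

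**4. What restores the error rate.**

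- *Cessation at one visit* (assumed quit proportion 0.22): marginal logistic model, leverage-corrected group-clustered standard errors, t on K − 2 degrees of freedom with K the number of groups. Type I error is 4.7% to 5.0% for m of 5, 10 and 12 and ICC 0 to 0.05. Without the correction, and with a normal reference, it is 5.2% to 6.2%.
- *Stress and depressive symptoms*, group and participant random intercepts: 4.0% to 5.3% for the arm effect averaged over visits (ICC 0.01 to 0.05). This does not carry over to other contrasts. At m = 12 and ICC 0.05 with a group effect that is not constant over visits, the last-visit effect is about 6% to 9% and the arm-by-time contrast about 10% to 24%. The group intercept cancels from a change over time, so visit-specific group deviations are treated as independent individual error. Analysis clustered on group stays near 5%.
- *Adding a group-by-visit random effect* supplies the missing variance component. That is a structural argument; no simulated rate is given for it, for clustered logistic models over repeated visits, or for race-by-arm contrasts under any of these remedies.

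**5. Cost in precision.** Widening at one time point = √DE × t(K − 2)/1.96 − 1. For m = 5, ICC 0.01, K = 100: √1.04 × 1.984/1.96 − 1 = 3.3%. For m = 12, ICC 0.05, K = 42: √1.55 × 2.021/1.96 − 1 = 28.4%.

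**The case against.** The strongest reply is that section 6 is a permissive menu that already contains generalized linear mixed models, so a competent analyst could fit a group effect within the plan. That is true, and a reader who inferred that the trial will ignore therapy group would go beyond the text. What remains is that the menu equally allows methods that ignore group, and that even choosing a mixed model settles nothing without a named group term (step 2).

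A second reply is that the size is wholly assumed. That also stands. At the low end the excess is half a percentage point, and at ICC 0 there is none. Listing group cohesion as a measure shows that the protocol regards groups as able to differ; it does not show that the ICC exceeds 0. Neither group size nor ICC has to be known, however, to put the term in the model.

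Third, absence can be asserted only for the text reviewed. Some text between the headings of sections 12 and 15 was not available, and the second site has its own protocol. Nor does the protocol describe the unit of randomisation beyond assigning participants, or its timing relative to group formation. Individual assignment is the natural reading, and clustering by delivery arises either way.

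**Conclusion.** The concern holds in a limited form. The plan permits arm comparisons that ignore therapy group, and no text reviewed says it will be modelled. For arm main effects a nominal 5% test would have a true error of 5.5% to 11.5%, given 5 to 12 per group and ICC 0.01 to 0.05. It should be fixed; confidence is moderate because the omission is plain but its size cannot be determined from the documents.

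Two stronger readings are not supported. One is that the disparities aim is compromised. Race-by-arm contrasts stay near nominal in mixed groups. Admitting people who "speak/read English and/or Spanish" makes language-specific groups possible, but group composition is not stated. The other is that the error rate is as high as 18.2%: that needs a participant-only model and a group effect fully constant over all four visits, at the top of the assumed range.

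**What to change.** Record the therapy group to which each randomised participant is assigned, including those who attend no session, since the Withdrawal of Subjects text commits to intention to treat and the Randomization paragraph accepts that attendance will be incomplete. Then state in section 6 that every arm comparison accounts for therapy group in both conditions:

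- **Cessation:** a marginal logistic model, at one visit or over repeated visits, with standard errors clustered on therapy group, a small-sample correction and degrees of freedom based on the number of groups.
- **Stress and depressive symptoms:** either the same corrected group-clustered standard errors, or a linear mixed model with participant and therapy-group random intercepts plus a group-by-visit random effect. Group and participant intercepts alone are adequate only for the arm effect averaged over visits.
- **Independent-observation tests:** keep these for baseline description.

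The cost is analysis wording and one identifier, easiest to record when groups are formed. Beyond the widening in step 5, some precision is lost even if the ICC is 0: intervals at one time point are about 1% to 3% wider with clustered standard errors and about 4% to 7% wider with a linear mixed model with a group intercept, whose test is then slightly conservative (3.8% to 4.2%). For the four-visit average with a fully constant group effect (m = 12, ICC 0.05, r = 0.3), intervals are up to 51% wider than from a participant-only model: √2.158 × 2.021/1.96 − 1. The marginal model is preferred for cessation because a logit mixed model changes the estimand to a conditional odds ratio.
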